## 1 LIST OF ABBREVIATIONS

Abbreviation	Description
AE	Adverse Event
CFR	Code of Federal Regulation
CRF	Case Report Form
EC	Ethics Committee
FDA	Food and Drug Administration
FIQ	First Impression Questionnaire
GAIS	Global Aesthetic Improvement Scale
GCP	Good Clinical Practice
HIPAA	Health Information Portability and Accountability Act
HM	Happiness Measures
ICF	Informed Consent Form
ICH	International Conference on Harmonization
IRB	Institutional Review Board
m	Meter
mg	Milligram
ml	Milliliter
OCR	Optimal Cosmetic Results
OCSS	Oral Commissure Severity Scale
PI	Principal Investigator
POLSS	Perioral Lines Severity Scale
SAE	Serious Adverse Event
SD	Standard Deviation
SHS	Subjective Happiness Scale
SOP	Standard Operating Protocol

## 2 PROTOCOL SYNOPSIS

Title	An Open-Label, Post-Market Study to Assess the Impact of Lip Rejuvenation with Restylane® Silk on Projected First Impressions and Mood Perceptions
Indication	Subjects with mild to severe oral commissures or none to severe perioral lines who request lip rejuvenation with Restylane® Silk
Sample Size	20
Number of Centers	One center in the United States
Study Objectives	The primary objective of this study is to determine if subjects who receive lip rejuvenation treatment with Restylane® Silk project a more positive first impression and report an improvement in mood perception.
Subject Selection	A total of 20 subjects who wish to receive lip rejuvenation treatment with Restylane® Silk and meet the specified criteria will be enrolled.
Study Design	
20 subjects with mild to severe oral commissures or none to severe perioral lines will be enrolled and injected with Restylane® Silk. Photographs will be taken prior to and 14 days after Optimal Cosmetic Results has been achieved, as judged by the investigator.
 
Changes in the projected first impression will be assessed by a total of 200 blinded evaluators rating the photographs of subjects from the baseline and from 14 days post achieving the Optimal Cosmetic Results. Changes in subjects' mood will be self-assessed through Subjective Happiness Scale and Happiness Measures questionnaires. Aesthetic alterations will be assessed by the investigator via the Global Aesthetic Improvement Scale, Oral Commissure Severity Scale, and the Perioral Lines Severity Scale as well as by the self-assessment of subjects using the Global Aesthetic Improvement Scale.
 
A schematic of the study design is presented in Appendix A.

---

**Study Duration**

Subjects will be followed for 14 days after a treatment that has produced Optimal Cosmetic Results.

---

**Clinical Hypothesis**

Subjects who are treated with Restylane® Silk for lip rejuvenation project a more positive first impression as compared to their pre-treatment baseline. Those who are treated with Restylane® Silk will also report a more positive mood perception after treatment as compared to pre-treatment.

### **4 BACKGROUND**

A first impression can be defined as the initial judgment made of a person without a prior familiarity. It has been well recognized that these zero-acquaintance impressions, which are formed within seconds of seeing a person, are greatly influenced by physical appearances. The perceived impression forms an image of personality, known as the *physical personality*, that induces a set of expectations and behaviors in others, which, in turn, impact the manner by which an individual is judged and treated in the society.

It has been suggested that 'attractive' individuals receive better judgments and treatments whereas those deemed 'unattractive' generally seem to elicit negative responses. Various clinical studies have also linked aesthetic enhancements, through surgical or non-surgical procedures, with improved projected first impressions. Remarkably, the self-perception of physical appearances also seems to affect the development of inherent personality. It has been elucidated that self-dissatisfaction due to craniofacial abnormalities can elicit low self-esteem^5 while non-surgical aesthetic enhancements may improve self-esteem and lead to a better quality of life. Thus, improvements of physical appearances can create a better projected first impression as well as a better self-satisfaction.

In the past decade, dermal fillers have become one of the most popular minimally invasive treatments for rejuvenation and body sculpturing. According to the American Society of Plastic Surgeons, over 1.6 million hyaluronic acid filler procedures were performed in 2013. Restylane® Silk (Galderma Laboratories, L.P.) is a hyaluronic acid injectable filler, which is approved by the FDA for submucosal implantation for lip augmentation and dermal implantation for correction of perioral rhytids. The goal of this study is to determine if lip rejuvenation of patients with mild to severe oral commissures or none to severe perioral lines using Restylane® Silk would lead to an improved projected first impression and self-perception of mood.

### **5 STUDY OBJECTIVES**

The primary objective of this study is to determine if lip rejuvenation with Restylane® Silk results in an improved projected first impression as well as an improved self-perception of mood.

The secondary objective is to evaluate aesthetic improvements after lip rejuvenation treatment with Restylane® Silk and assess relations to any alternations in the projected first impression

and mood perception.

## 6 STUDY DESIGN

This is an open-label, post-market study to assess the impact of lip rejuvenation with Restylane® Silk on the projected first impression and the self-perception of mood.

20 subjects, at least 21 years of age, who display mild to severe oral commissures or none to severe perioral lines, as judged by the Principal Investigator (PI) utilizing the Oral Commissure Severity Scale (OCSS, Appendix G) or the Perioral Lines Severity Scale (POLSS, Appendix H), will be enrolled.

The study is composed of up to 4 patient visits and a post-visit evaluation of patients' photographs by blinded evaluators. A schematic of the study design is presented in Appendix A.

All subjects who meet the specified criteria, listed in Section 7, will complete the Subjective Happiness Scale (SHS, Appendix B) and the Happiness Measures questionnaire (HM, Appendix C) prior to receiving any treatments. The PI also records the severity of subjects' oral commissures and/or the perioral lines using the OCSS and/or the POLSS respectively. Furthermore, all subjects undergo photo- and videography, as described in Appendix I, prior to treatment.

Subjects will then be injected with Restylane® Silk with a volume sufficient to achieve Optimal Cosmetic Results (OCR), per treating investigator's discretion but not to exceed a total of 4ml (4 syringes). Subjects will be assessed 14 ± 3 days after injection for achieving the OCR. If OCR has not been reached, as judged by the PI, a second, 'touch-up,' injection of Restylane® Silk will be performed.

The final evaluation of subjects will take place 14 ± 3 days after achieving OCR. Hence, this would be 14 ± 3 days after the first injection for those who achieved OCR with one treatment but 28 ± 3 days after the first injection for those who required a 'touch-up' injection. Subjects will complete the SHS and HM questionnaires as well as self-report any aesthetic alterations experienced using the Global Aesthetic Improvement Scale (GAIS, Appendix D). They will also undergo photo- and videography, as described in Appendix I. Furthermore, the PI will rate the subjects on the GAIS (Appendix E) as well as on the OCSS and the POLSS.

Photographs taken at pre-treatment and 14-Day Post-OCR will be randomly divided into 4 binders, for a total of 10 photographs per binder. Each binder will be evaluated at least by 50 blinded evaluators using the First Impressions Questionnaire (FIQ, Appendix F) to rate each photograph.

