
## 7 SUBJECT SELECTION

A total of 20 subjects who meet all of following inclusion criteria and none of the exclusion criteria will be enrolled in this study.

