## **10 RESPONSE CRITERIA**

### **10.1 Primary Variable Assessments**

The primary assessment of this study is to determine if subjects who receive lip rejuvenation treatment with Restylane® Silk would project a more positive first impression as well as experience a more positive mood perception as compared to their baseline. The primary efficacy will be established by comparing the projected first impression of subjects at 14-Day Post-OCR with that of the baseline. The change in mood perception will be determined by comparing the SHS and HM results from 14-Day Post-OCR with those from the baseline.

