#### **10.1.1 Assessment of First Impressions**

Upon completion of the study, a minimum of 200 blinded evaluators will assess one of four binders, for a minimum of 50 blinded evaluators per binder, each comprised of 10 photographs selected randomly from Visit 1 (baseline) or Visit 4 (14-Day Post-OCR) for each subject. The

FIQ will be completed by each evaluator for each photo (see Appendix F). Each photograph will be graded based on a 10-point numerical rating scale for each of the 8 categories listed below:

- *Social skills*: Social desirability, temperament, positive mood, getting along with others, friendliness
- *Academic performance*: Intelligence, educational skills
- *Dating success*: Frequently invited, lack of dating anxiety, thought of positively after dating encounter
- *Occupational success*: Job performance, competence, motivation for success, suitability as potential employee
- *Attractiveness*: Pleasing appearance
- *Financial success*: Has achieved or is a member of an elevated socioeconomic status
- *Relationship success*: Willingness to compromise put the relationship health before their own desires or gain, Ability to maintain long term friendships
- *Athletic skills*: Ability to excel at athletic events, including individual and team sports

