## 12 STATISTICAL METHODS

### 12.1 Sample Size

20 subjects will be enrolled as described in Section 7. Using the primary end point of FIQ scores, and assuming a standard deviation of 14 and a difference of 2.5 in the total FIQ score between the baseline and 14-Day Post-OCR, a sample size of 20 will provide a power of approximately 8% (with  $\alpha=0.05$ ).

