### Instructions:

Step	Description
1	Please evaluate the following photographs in the books provided.
2	Complete the questionnaire for EACH photograph based on your FIRST impression.
3	EACH sheet is double-sided, so flip page to backside to complete next patient.
4	Hand the completed questionnaires and books back to study specialist.

Photo ID: **2**

Your Initials: \_\_\_\_\_

[figure not shown]

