## Appendix I Standard Operating Protocol for Photo- and Videography

### Photography and Poses

- Use the grid feature on any of these viewers to ensure the Frankfort Plane (imaginary line from tragus to infraorbital rim) is parallel to the floor.
- Stand approximately 1.5 m from patient with the camera in a portrait position.
- Ensure the patient has a relaxed expression and that lips are closed and eyes are open for each photo.
- Give instructions like, “Slowly move your chin down” or “Slowly turn your nose to the left” to achieve the desired poses listed below
- Standard Poses (all at 1.5 m)
  1. Frontal  
Make sure the patient doesn’t have their chin high or low by checking the Frankfort Plane. For this view, the line on the viewfinder should extend from the right tragus, across both infraorbital rims and across the left tragus. This should be parallel to the floor.
  2. 45° Left  
For this view, the tip of the nose should line up with the edge of the cheek.
  3. Left Profile  
For this view, ensure the patient is not rotated to the left or right (hint: look at the eyebrows to see how much of the glabella you see).
  4. 45° Right  
For this view, the tip of the nose should line up with the edge of the cheek.
  5. Right Profile  
For this view, ensure the patient is not rotated to the left or right (hint: look at the eyebrows to see how much of the glabella you see).

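### Unrestricted random division of the photographs into binders leaves the before/after mix per binder to chance, so evaluator-group leniency adds small but avoidable error to the primary FIQ change

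*Combined protocol and SAP*

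**What the plan says.** Section 7 enrols 20 subjects, so there are 40 photographs if one is used per subject and time point. Section 6 allocates them as follows: "Photographs taken at pre-treatment and 14-Day Post-OCR will be randomly divided into 4 binders, for a total of 10 photographs per binder". Section 10.1.1 describes the binders as "each comprised of 10 photographs selected randomly from Visit 1 (baseline) or Visit 4 (14-Day Post-OCR) for each subject", and says that "a minimum of 200 blinded evaluators will assess one of four binders, for a minimum of 50 blinded evaluators per binder".

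Section 10.1 makes this rating the basis of efficacy: "The primary efficacy will be established by comparing the projected first impression of subjects at 14-Day Post-OCR with that of the baseline". Section 12.3.1 lists the FIQ first among the primary endpoints.

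Section 12.4 plans descriptive statistics and two-sided testing at 0.05. It names no model and no term for evaluator, binder or page position. Nowhere do the documents fix the before/after ratio in a binder, say whether a subject's two photographs may share one, set or rotate page order, or say how evaluators are assigned to binders. Appendix I lists five standard poses, and the one shown to evaluators is not named.

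**The concern.** Evaluators differ in how generously they score. Each sees only one binder, so a subject's baseline and post-treatment photographs are usually scored by different people. The difference between evaluator groups then enters that subject's change. Without adjustment, it is certain to cancel from the mean change only if every binder holds as many baseline as post-treatment photographs. Simple random division does not ensure that, and the binders are made once, so an uneven split stays for the whole rating exercise.

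Two results are exposed: the mean FIQ change, and the subject-level changes. Section 5 needs the latter, because its secondary objective relates aesthetic improvement to alterations in first impression.

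**Working it through.** **Inputs from the documents.** 20 subjects (Section 7); 4 binders of 10 photographs (Section 6); at least 50 evaluators per binder (Section 10.1.1); for the total FIQ score, "assuming a standard deviation of 14 and a difference of 2.5", with alpha 0.05 and power of about 8% (Section 12.1).

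**Input assumed.** The documents give no between-evaluator SD of the total FIQ score. I take 5 to 10 points on the 8-80 total.

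**The plan's own figure.** Two independent groups of 20, difference 2.5, SD 14, two-sided 0.05: standard error 14 × √(2/20) = 4.43 and power 8.1% (8.5% with the t distribution). This reproduces the stated 8%. Treated as paired with SD of differences 14, the standard error is 14/√20 = 3.13 and power is 11.8%. I use 3.13 as the yardstick because it is the stricter one.

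**How uneven the binders are, literal text of Section 6** (40 photographs divided at random into 4 × 10):
- Same binder for a subject's two photographs: 9/39 = 23%. On average 20 × 30/39 = 15.4 subjects are split across binders.
- All four binders 5:5: [20!/(5!)⁴]² ÷ [40!/(10!)⁴] = 2.9%.
- At least one binder 7:3 or worse: 64%.

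**Alternative reading of Section 10.1.1** (each subject once per binder, complementary binders, time point drawn at random per subject):
- One pair of binders 5:5: C(10,5)/2¹⁰ = 24.6%. Both pairs: 0.246² = 6%.
- At least one pair 7:3 or worse: 1 − (1 − 0.344)² = 57%.

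**Effect on the mean change.** Let L_b be the mean leniency of the group rating binder b, with SD = evaluator SD/√50. The contribution to the mean change is Σ L_b × (after_b − before_b)/20.
- Literal text: the number of post-treatment photographs in a binder has variance 10 × ¼ × 30/39 = 1.92, so after_b − before_b has variance 7.69. The multiplier on SD(L_b) is √(4 × 7.69)/20 = 0.277.
- Alternative reading: the variance of the difference is 10 and the two binders of a pair mirror each other. The multiplier is √(2 × 2 × 10)/20 = 0.316.

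| Assumed evaluator SD | SD of L_b | Mean change, literal | Mean change, alternative | One split subject (√2 × SD of L_b) |
|---|---|---|---|---|
| 5 | 0.71 | 0.20 | 0.22 | 1.0 |
| 10 | 1.41 | 0.39 | 0.45 | 2.0 |

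**Against the yardstick.** √(3.13² + 0.45²) = 3.16, an increase of about 1% at the top of the range.

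**After balancing.** With 5 baseline and 5 post-treatment photographs in every binder, after_b − before_b = 0 and the contribution to the mean change is 0. The last column of the table is unchanged.

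**The case against.** The strongest reply is that this hardly matters. The allocation is random, so the error has mean zero and is variance, not bias in a known direction. It raises the paired planning standard error by about 1% at most over the assumed range, in a study with about 8% planned power and a descriptive analysis. A binder term in the analysis would also deal with it. All of this stands as to size. It does not defend the stated rule, because Section 12.4 plans no such term and a balanced allocation costs nothing.

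Three stronger readings are tempting and are not supported.

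- A reader might infer a large shift in the primary result. For example, a 7:3 split in the same net direction in both pairs, with a 2-point group difference, moves the mean by 0.4 × 2 = 0.8 points against the planned 2.5. That is a tail case. Under the alternative reading, a leniency error of 0.8 or more in either direction has probability about 0.6% at evaluator SD 5 and 8% at SD 10.
- A reader might infer that pose is drawn at random. Sections 6 and 10.1.1 apply randomness to the binders and the visit, not to pose. Appendix I takes the same five poses at every session, so matched poses are available; the pose is simply not named.
- A reader might infer that page order is random, or fixed for all evaluators. Appendix F has numbered photographs in books and double-sided questionnaire sheets, which makes a common order within a binder plausible. No section states it.

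**Conclusion.** The point holds as a cheap design improvement, not as a threat to the study's conclusion. Both readings of the allocation leave the before/after mix to chance, and nothing in the analysis repairs it. The avoidable error in the mean FIQ change has SD about 0.2 to 0.45 points, small beside 3.13. The effect on individual changes is larger, SD 1 to 2 points for each subject split across binders, and it bears on the planned relation between aesthetic and first-impression change.

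These figures assume a between-evaluator SD of 5 to 10 points, leniency that is additive, and evaluators who reach binders as if at random. If they do not (for instance, if one binder goes mainly to one kind of evaluator), the group difference no longer shrinks with 50 raters and an uneven split could bias the change systematically. The documents do not say how evaluators are assigned.

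**What to change.** In Sections 6 and 10.1.1, replace the simple random division by restricted randomisation:

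- Divide the subjects at random into two sets of 10 and make two complementary binders per set. Each subject appears once in each binder of the pair, and each binder holds 5 baseline and 5 post-treatment photographs.
- Give a subject the same page position in both binders, or counterbalance the order.
- Assign evaluators to binders at random and say so.
- As a clarification only, name one pose to be used at both visits.

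The balance removes additive group leniency from the mean change. It does not remove it from individual subjects' changes, so the secondary analysis should acknowledge that error or adjust for evaluator group.

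The cost is one paragraph of protocol text and a short randomisation list, with no extra visits, photographs or evaluators. It has to be settled before the binders are made, because the allocation cannot be rebalanced after rating.

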
## 7 SUBJECT SELECTION

A total of 20 subjects who meet all of following inclusion criteria and none of the exclusion criteria will be enrolled in this study.

## 7.1 Inclusion Criteria

All subjects must meet the following inclusion criteria:

1. Subject is an adult of at least 21 years of age;
2. Subject has mild to severe oral commissures or none to severe perioral lines, as assessed by the treating investigator;
3. Subject is willing and able to provide written informed consent prior to the performance of any study related procedure;
4. Subject is willing and able to comply with the protocol requirements; and
5. Subject is willing and able to provide written photo consent and adhere to the photography and video procedures such as removal of jewelry and makeup.

## 7.2 Exclusion Criteria

Subjects meeting any of the following criteria will be excluded from the study:

1. Subjects who have received lip filler treatments in the past 12 months or neurotoxin injections in the past 6 months;
2. Subjects who plan to undergo neurotoxin treatments, ablative skin treatments, facial cosmetic surgery, or other injectable filler treatments during the course of the study;
3. Subjects with a known allergy or sensitivity to any component of the study ingredients;
4. Subjects with a history of bleeding disorders;
5. Female subjects who are pregnant or nursing as well as those who are of childbearing potential but do not employ adequate birth control methods;
6. Subjects with severe allergies manifested by a history of anaphylaxis or presence of multiple severe allergies;
7. Subjects with previous history of sensitivity to amide type local anesthetics;
8. Current history of chronic drug or alcohol abuse;
9. Concurrent therapy that, in the investigator's opinion, would interfere with the evaluation of the safety or efficacy of the study product;
10. Subjects who, in the investigator's opinion, have a history of poor cooperation, non-compliance with medical treatment, or unreliability; and
11. Enrollment in any active study involving the use of investigational devices or drugs.

## 8 TREATMENT AND STUDY SUPPLIES

### 8.1 Description of Study Supplies and Handling

Restylane® Silk (Galderma Laboratories, L.P.) is a gel of hyaluronic acid produced by the *Streptococcus* species of gram-positive bacteria that is chemically crosslinked with butanediol diglycidyl ether (BDDE) and suspended in phosphate buffered saline (pH 7) at a concentration of 20 mg/ml with 0.3% lidocaine. Restylane® Silk supplies are stored in a secure cabinet at room temperature at the investigation site.

## 8.2 Packaging and Labeling

Restylane® Silk is supplied in disposable glass syringes with a Luer-Lok® fitting and is co-packed with a sterilized 30 G x ½ needle. Each syringe contains 1 ml of the injectable gel (20 mg/ml of hyaluronic acid) with 0.3% lidocaine. Each package is for single patient use. A patient record label, which is included in the syringe label, will be attached to each patient's records for product traceability.

## 8.3 Method of Application

### 8.3.1 Pre-treatment Guidelines

Prior to treatment, the patient is advised to avoid taking aspirin, nonsteroidal anti-inflammatory medications, St. John's Wort, and high doses of vitamin E supplements 14 days prior to the day of treatment, as these agents may increase bruising and bleeding at the injection site.

